9.0 Missing data

Participants who are unable to be classified into a diet group will be excluded from the study, such as when participants answered "do not know" or "prefer not to say" to all questions on meat or fish intake, or when participants did not complete these questions. Participants with no hospital record will be excluded. Participants with missing covariate data will be excluded from the main analyses unless the amount of missingness substantially compromises statistical power, in which case unknown categories will be formed for each covariate.

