3.0 Data cleaning

3.1 Exclusion criteria

Participants will be excluded from all analyses for any of the following reasons:

- Unable to link dietary and lifestyle data with hospital data (e.g. no NHS number provided and unable to match with records).
- Had a hip fracture (World Health Organisation, WHO International Classification of Disease (ICD-10) codes S72.0-S72.2) or osteoporosis (ICD-10 codes M80-M82) before or on the date of recruitment.

- Outlier diet or anthropometric data (energy intake < 500 or > 5000 kcal/day or BMI < 10 or > 60 kg/m²)
- Withdrew consent during the study period.
- Biological sex assigned at birth differed to self-reported sex at recruitment.
- Unable to be classified into a diet group (e.g. responded “do not know” or “prefer not to say” for questions on meat or fish intake).

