5.0 Outcomes

The primary outcome will be first incidence of hip fracture (ICD-9 code 820 and ICD-10 codes S72.0-S72.2) identified using hospital inpatient data for England, Scotland, and Wales. This includes Hospital Episode Statistics for England until 30th September 2021, Scottish Morbidity Records for Scotland until 31st July 2021, and the Patient Episode Database for Wales until 28th Feb 2018. The timeframe will be person-years until hip fracture incidence, or until end of study period or death in non-cases, calculated as age at time of event or censoring minus age at study entry. Sources and dates of availability for each region’s hospital inpatient data (and therefore censoring dates) are presented in Table 2.

Table 2: Hospital inpatient data in England, Scotland, and Wales.

Country	Data source	Period of time for which data is available
England	Hospital Episode Statistics (HES)	1997 – 30 th Sept 2021
Scotland	Scottish Morbidity Record (SMR)	1981 – 31 st July 2021
Wales	Patient Episode Database for Wales (PEDW)	1998 – 28 th Feb 2018

Adapted from: [External Info : Data providers and dates \(ox.ac.uk\)](#)

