6.0 Sample size

The minimum detectable hazard ratio for potential associations between each diet group and hip fracture risk (with regular meat-eaters as the reference group) was estimated in Stata (v17.0) assuming the following parameters:

- Total sample size of 472,337 participants, including 247,571 regular meat-eaters, 205,385 occasional meat-eaters, 10,696 pescatarians, and 8685 vegetarians, as has been previously reported in a UK Biobank publication on risk of cancer in these diet groups (1). Numbers of participants in each diet group in our study may differ slightly to the cited UK Biobank study due to differences in exclusion criteria.

- Hip fracture incidence of 3%.
- $p < 0.05$.
- 80% power.
- A theoretical standard deviation of the exposure (diet group) calculated based on the percentage of participants in each diet group (Table 3).

Table 3: Minimal detectable hazard ratios for associations between diet groups and hip fracture risk with regular meat-eaters as the reference group.

Diet group	SD	Minimum detectable HR
Regular meat-eaters	Ref	Ref
Occasional meat-eaters	0.50	1.05
Pescatarians	0.20	1.17
Vegetarians	0.18	1.19
Vegans	0.04	1.82

SD = Standard deviation. HR = Hazard ratio. The SD for dietary group is theoretical and has arbitrary units.

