8.0 Statistical modelling

8.1 Main analyses

8.1.1 Absolute risk difference

To estimate the population impact of being in each diet group on hip fracture incidence, we will determine the absolute risk difference for hip fracture between each diet group and regular meat-eaters (reference group) per 1000 people over 10 years. This will be calculated as the crude differences between the predicted incidence per 1000 people over 10 years between each diet group and the regular meat-eaters, using hazard ratios and 95% confidence intervals expressed as floating absolute risks, as described elsewhere (2).

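### Section 9.0 excludes people with no hospital record, which is wider than failed linkage; taken literally it removes only non-cases and inflates incidence and the 10-year absolute risks

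*SAP*

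**What the plan says.** The SAP has two exclusion rules that involve hospital data.

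- Section 3.1 (Exclusion criteria) removes people on grounds of linkage: "Unable to link dietary and lifestyle data with hospital data (e.g. no NHS number provided and unable to match with records".
- Section 9.0 (Missing data) states, without qualification: "Participants with no hospital record will be excluded".

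The term hospital record is not defined. Three other sections bear on the point.

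- Section 5.0 defines the outcome as a first hip fracture "identified using hospital inpatient data for England, Scotland, and Wales", with person-years running to the fracture "or until end of study period or death in non-cases".
- Section 8.1.1 places among the main analyses the "absolute risk difference for hip fracture between each diet group and regular meat-eaters", computed as "crude differences between the predicted incidence per 1000 people over 10 years between each diet group and the regular meat-eaters".
- Section 6.0 plans on a "Total sample size of 472,337 participants" and a 3% incidence, and says that group sizes "may differ slightly to the cited UK Biobank study due to differences in exclusion criteria".

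**The concern.** The two rules describe different people. When linkage fails, the outcome is unknown and exclusion is reasonable. When linkage succeeds and there is no admission, the outcome is known: no hip fracture was recorded in hospital. Such people belong in the denominator.

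Because cases come only from inpatient data, no case can lack a hospital record. The section 9.0 rule, coded as written, can therefore remove only non-cases. The number of events stays the same and event-free person-time is lost, so incidence and 10-year absolute risks are overstated and the risk differences are distorted.

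The rule also selects partly on the future. Hospital data start between 1981 and 1998 and recruitment was in 2006–2010, so a person may qualify through an admission before or after entry. Keeping people because they were admitted during follow-up conditions the cohort on events after baseline. If the chance of having any record differs by diet group after adjustment, the hazard ratios move too.

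**Working it through.** **Inputs from the SAP**

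- N = 472,337 (section 6.0). The four groups add up to it: 247,571 + 205,385 + 10,696 + 8,685 = 472,337.
- Incidence 3% (section 6.0), so events = 0.03 × 472,337 ≈ 14,170.
- HR 1.19 for vegetarians (Table 3), used only as an example.
- Data windows from Table 2.

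**Assumed:** q, the share of linked participants with no hospital record. The SAP gives no value, so a range is shown.

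**1. Incidence.** Events are unchanged and the denominator becomes N(1 − q), so incidence = 0.03/(1 − q). The number dropped is 472,337 × q.

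| q | Incidence | Dropped |
|---|---|---|
| 0 | 3.00% | 0 |
| 5% | 3.16% | 23,617 |
| 10% | 3.33% | 47,234 |
| 20% | 3.75% | 94,467 |
| 30% | 4.29% | 141,701 |

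If the share is instead defined among non-cases only (f), incidence = 0.03/(0.03 + 0.97(1 − f)). This gives 3.15%, 3.32%, 3.72% and 4.23% at 5%, 10%, 20% and 30%, which is almost the same.

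**2. Absolute risk difference.** For illustration, take a reference risk of 30 per 1000 and HR 1.19, with equal q in both groups, and read the HR as a risk ratio:

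- no exclusion: 30 × 0.19 = 5.7 per 1000
- q = 10%: 5.7/0.9 = 6.3 per 1000
- q = 20%: 5.7/0.8 = 7.1 per 1000

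**3. Hazard ratio.** Each group's rate is multiplied by about 1/(1 − q), so the HR is multiplied by about (1 − q_ref)/(1 − q_group). With equal q the factor is 1. With a true HR of 1.00:

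- 10% in the reference, 12% in the comparison group: 0.90/0.88 = 1.02
- 20% against 22%: 0.80/0.78 = 1.03
- 20% against 25%: 0.80/0.75 = 1.07

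**4. Check by simulation.** The set-up was 4 million people per group, 12 years of follow-up, 3% cumulative fracture and competing death, with the exclusion applied to non-cases only. With 20% excluded in both groups, the rate rose 1.245-fold and the HR was 1.185 before and after. With 20% against 25% and a true HR of 1.00, the estimate went from 1.001 to 1.067. Both agree with the formulas.

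**5. Region.** From start year to end date, the Table 2 windows are about 19.2–20.2 years for Wales, 23.7–24.7 for England and 39.6–40.6 for Scotland. The chance of having any record therefore depends on region as well as on health.

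Table 3 is not in question: its hazard ratios for occasional meat-eaters, pescatarians and vegetarians reproduce from the plan's own inputs (1.05, 1.17 and 1.19).

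**The case against.** The strongest counter-argument is that section 9.0 is shorthand for failed linkage. It stands under missing data, the sentence before it also restates a section 3.1 exclusion, and section 3.1 itself speaks of matching with records. Never having been admitted is not among the reasons listed in section 3.1. Section 5.0 follows non-cases to death or the end of study with no admission condition. Losing tens of thousands of people would also fit poorly with group sizes that differ only slightly from the cited study. On that reading there is no bias.

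This is plausible, and probably what was meant. It does not settle the matter, because no sentence defines the term or expressly keeps linked, never-admitted participants. Section 11.1.4 also uses hospital records to mean dated diagnoses, not linkage status, so an analyst could reasonably code the exclusion as absence of any episode.

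The objections to the numbers are fair but small.

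- Every q is assumed, and the hazard-ratio shifts need a second assumption, that q differs between diet groups. The SAP supports neither a size nor a direction.
- The 3% has no stated time span, so using 30 per 1000 as a 10-year risk is only illustrative.
- Treating the HR as a risk ratio gives 5.7 per 1000; under proportional hazards it is 1000 × (1 − 0.97^1.19) − 30 = 5.6.
- Region is a listed potential confounder (section 8.1.3), which weakens the regional argument for the hazard ratio.

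None of these changes the direction of the effect on incidence.

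**Conclusion.** The point holds. Section 9.0 states a rule that differs from section 3.1 and, followed as written, gives a wrong cohort. It would raise incidence and absolute risks by a factor of about 1/(1 − q): roughly 5% at q = 5%, 11% at 10% and 25% at 20%. Hazard ratios would be unaffected if q were equal across diet groups after adjustment, and would shift by about 2% to 7% for the differences of 2 to 5 percentage points shown.

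That the rule removes only non-cases follows directly from section 5.0. The size of the effect rests on assumed q. If the authors meant failed linkage, the results are unaffected and only the wording is wrong. The correction should be made in either case, because the sentence bears on a main-analysis estimate.

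**What to change.** Replace the sentence in section 9.0 with wording such as:

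> Participants for whom linkage to hospital data could not be established (section 3.1) will be excluded. Linked participants with no inpatient episode are retained as non-cases and censored at death or at the regional end date.

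In section 3.1, add that inability to match with records means failed identifier linkage, not absence of an admission.

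The cost is one replaced sentence and one short clarification. No new data are needed, and the change agrees with the follow-up rule for non-cases in section 5.0.

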10.0 Timescales

Target analysis completion date (excluding manuscript preparations): Mar 2023.

11.0 Additional information

Fig S1: Equation used to calculate theoretical standard deviations for diet group analyses.

$$SD = [p(1 - p)]^{0.5}$$

Where SD = standard deviation and p = percentage of participants in the vegetarian category (as a decimal).

11.1 Covariate classification

11.1.1 Socio-demographics

Age at recruitment

Calculated as date of recruitment minus date of birth, truncated to whole year.

Sex

Genetic sex as determined from genotyping analysis.

Region

At recruitment, participants attended one of 22 assessment centres across the UK. We will group the centres into three regions as follows: England (Barts, Birmingham, Bristol, Bury, Croydon, Hounslow, Leeds, Liverpool, Manchester, Middlesbrough, Newcastle, Nottingham, Oxford, Reading, Sheffield, Stockport, Stoke), Scotland (Edinburgh, Glasgow), and Wales (Cardiff, Swansea, and Wrexham).

Ethnicity

At recruitment, participants were asked in the touchscreen questionnaire to select their ethnic group among "White", "Mixed", "Asian or Asian British", "Black or black British", "Chinese", "Other ethnic group", "Do not know", or "Prefer not to say". We will regroup participants into the following ethnicity categories: White, Mixed race, Asian, Black, Other, and Unknown.

Socio-economic status

Townsend deprivation index will be used to represent socio-economic status. This variable has been created in the UK biobank based on the preceding national census output areas. Each participant was assigned a score corresponding to the output area in which their postcode was located. Participants

will then be split into quintiles from least deprived (Q) to most deprived (Q5), with an additional category for missing data (where postcode information was not provided).

Living alone

In the touchscreen questionnaire at recruitment, participants were asked “Including yourself, how many people are living together in your household?”. From this, we will define the variable “live alone” (with options yes, no, unknown).

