8.1.3 Accounting for confounding

Unadjusted and adjusted cox models will be applied. Both will control for age by using attained age as the timescale. The adjustment set for the adjusted model will be informed by a DAG model, which will be constructed using the online tool DAGitty, following available guidelines on their use (3). Confounders will be considered as covariates that are 1) risk factors of the outcome; 2) associated with the exposure; and 3) not on the causal pathway (4). Potential confounders are age at recruitment, sex, region, ethnicity, socio-economic status or education, marriage, physical activity, smoking, alcohol, BMI (or height and weight), number of children, menopausal status, hormone replacement therapy (HRT) in postmenopausal women, chronic disease prevalence at recruitment, and use of nutritional supplements (either generic or supplement-specific e.g. for calcium, vitamin D, and fish oil in particular, depending on availability of data). A list of likely confounders and their derivation is summarised in Supplementary Table 1.

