8.2 Subgroup analyses

We will stratify the adjusted model by potential effect modifiers, and will add these covariates to adjusted models as interaction terms with diet group independently, using likelihood ratio tests comparing regression models with and without interaction terms to test for effect modification.

To investigate the role of diet quality as a potential effect modifier, participants will be dichotomised into higher and lower AHEI adherence groups at the median AHEI score in the overall sample to maximise power in each diet group sub-strata. We will also assess the interaction between diet groups and a five-unit increase in AHEI score on hip fracture risk. Other potential effect modifiers include age (continuous and split at < 60 years, ≥ 60 years), sex (male, female), and BMI (continuous and split at < 18.5, 18.5-24.9, and ≥ 25 kg/m² if there is enough power).

The adjusted model will also be further stratified by specific single-nucleotide polymorphisms (SNPs) of genes with a plausible relationship with hip fracture risk and diet (PPAR γ , VDR, MTHFR, CYP24A1, CYP27B1, and IGF-1) to explore potential gene-diet interactions.

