8.4 Sensitivity analyses

1. An adjusted model with BMI removed from the adjustment set will be presented to determine the contribution of weight management to any associations.
2. We will present an adjusted model with vegans and vegetarians separated to determine if excluding vegans from the vegetarian group alters potential associations with hip fracture risk.
3. Online follow-up 24-hour dietary recall data will be compared with touchscreen FFQ data at recruitment to check for changes in diet group over time. In cases of substantial exposure change over time (e.g., > 10% of participants changing their dietary group), models will be repeated restricted to participants who maintained their original diet group.
4. Excluding cases occurring in the first three years of follow-up to check for reverse causality.
5. Excluding participants on long-term treatment for illnesses at recruitment who may be generally unhealthier and therefore at a higher risk of hip fracture.

6. We will explore patterns of missing covariate data, and will use multiple imputation through Stata's 'mi' package in the event of substantial missing covariate data.

All analyses will be performed using Stata. Two-sided p values < 0.05 will be considered statistically significant. All analyses performed and effect sizes computed will be presented in resulting manuscripts to avoid bias in selection of the reported result.

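### Sex is taken only from genotyping, so by default participants without usable genotype data leave an adjusted primary analysis that needs no genetics

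*SAP*

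**What the plan says.** - **Definition of sex.** SAP section 11.1.1 gives a single source: "Genetic sex as determined from genotyping analysis". It names no alternative source and no level for unknown sex. In the same section, ethnicity and living alone have an unknown level and deprivation has a category for missing data.
- **Role of sex.** Section 8.1.3 lists it among the candidates for adjustment: "Potential confounders are age at recruitment, sex, region, ethnicity". The final set is to be informed by a DAG. Section 8.2 also names sex as an effect modifier.
- **Missing covariates.** Section 9.0: "Participants with missing covariate data will be excluded from the main analyses unless the amount of missingness substantially compromises statistical power". When that exception applies, every covariate is instead given a level for unknown values. Section 8.4, item 6, adds that the authors "will use multiple imputation through Stata's 'mi' package in the event of substantial missing covariate data", but as a sensitivity analysis.
- **Other sex information held.** Section 3.1 excludes a participant if "Biological sex assigned at birth differed to self-reported sex at recruitment", so a self-reported sex exists outside the genetic data.
- **Where genetics is needed.** Diet group comes from the touchscreen questionnaire (section 4.2) and hip fracture from hospital inpatient data (section 5.0). Only the gene-diet analyses (sections 1.2 and 8.2) need genotypes.

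**The concern.** Sections 11.1.1 and 9.0 are harmless when read separately. Together they make a usable genotype an unstated entry condition for the adjusted primary analysis. A participant with a classified diet, linked hospital data and a recorded sex would be dropped because the chosen source for sex happens to be missing.

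What is at stake is some precision, and a primary cohort selected on having given a usable genetic sample. The effect also reaches the diet-quality analysis, because the wholegrain and alcohol components of the AHEI are scored separately for men and women. The loss is avoidable, since the same information is held from recruitment.

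**Working it through.** **Inputs.** From SAP section 6.0: 247,571 regular meat-eaters, 205,385 occasional meat-eaters, 10,696 pescatarians and 8,685 vegetarians (total 472,337); incidence 3%; power 80%. From section 8.4: two-sided 5% significance. From Fig S1: SD = √[p(1 − p)]. The fraction *f* without usable genotype data is not in the SAP; 1% to 5% is assumed.

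**Step 1: reproduce Table 3.** Minimum detectable HR = exp[(1.960 + 0.842) / (SD × √(0.03 N))], where N is the diet group plus regular meat-eaters.

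- Occasional: N = 452,956, SD 0.498 (stated 0.50). With 0.50, HR = 1.049 (stated 1.05).
- Pescatarian: N = 258,267, SD 0.199 (stated 0.20). With 0.20, HR = 1.173 (stated 1.17).
- Vegetarian: N = 256,256, SD 0.181 (stated 0.18). With 0.18, HR = 1.194 (stated 1.19).

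These three rows reproduce. The vegan row cannot be checked fully because no vegan count is given.

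**Step 2: size of the loss.** Participants lost = 472,337 × *f*. Cases lost = 472,337 × 0.03 × *f*, from 14,170 expected. Vegetarian cases lost = 8,685 × 0.03 × *f*, from about 261. Power at the design point = Φ[2.802 × √(1 − *f*) − 1.960].

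| *f* (assumed) | Participants lost | Cases lost | Vegetarian cases lost | Power | Vegetarian detectable HR |
|---|---|---|---|---|---|
| 0 | 0 | 0 | 0 | 80.0% | 1.194 |
| 1% | 4,723 | 142 | 3 | 79.6% | 1.195 |
| 3% | 14,170 | 425 | 8 | 78.8% | 1.198 |
| 5% | 23,617 | 709 | 13 | 78.0% | 1.200 |

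**Step 3: who is lost.** With the same *f* in every group, the share falling on regular and occasional meat-eaters is (247,571 + 205,385) / 472,337 = 95.9%.

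**Step 4: would the exception in section 9.0 apply?** It needs a substantial loss of power and sets no threshold. A fall of 0.4 to 2.0 percentage points is unlikely to qualify on its own, so the default exclusion would stand. If missingness in other covariates did trigger it, the result would be an unknown-sex category for people whose sex was recorded at recruitment.

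**Step 5: what does the genotype add?** Section 3.1 removes people whose biological and self-reported sex differ. If biological sex there means genotyped sex, the two variables already agree in everyone retained who has both, and requiring the genotype adds no accuracy for them.

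**The case against.** The strongest reply is that this is housekeeping. The SAP never says that anyone lacks genotype data, so the existence of the loss is inferred as well as its size. Even at 5%, the vegetarian detectable HR moves by only 0.006 and no planned conclusion changes. Sex is not the only covariate without an unknown level either: BMI, physical activity, number of children and menopausal status have none. All of this stands and keeps the point minor. Sex differs because section 3.1 shows that another source is already held.

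Four stronger readings are tempting, and the document does not support them.

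- *That exclusion is certain.* It is the default. Section 9.0 has its unknown-category exception, and does not say whether missingness is judged per covariate or summed over all of them. Section 8.4 adds imputation as a sensitivity analysis.
- *That the loss falls mainly on the small diet groups.* Nothing suggests that missing genotypes concentrate there. Under a proportional loss, about 96% of those dropped are meat-eaters; vegetarians would lose 3 to 13 of the 140 to 710 cases.
- *That the genotype is redundant outright.* Section 3.1 does not name genetic sex, so this depends on what biological sex means there.
- *That the hazard ratios will be biased.* This would need genotype availability to relate to fracture beyond the adjustment covariates, and differently by diet group. The SAP gives no evidence of that.

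**Conclusion.** The point holds as a minor one. As written, sections 11.1.1 and 9.0 by default remove participants without usable genotype data from an adjusted primary analysis that uses no genetic information. If 1% to 5% are affected, about 4,700 to 23,600 participants and 140 to 710 expected cases are lost, and power at the design point falls from 80% to between 79.6% and 78.0%. The gain from changing this is a little precision and a more representative cohort, not the rescue of an underpowered study.

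The conclusion assumes that some participants lack genotype data (the SAP gives no count), that the loss is proportional across diet groups, that the 3% incidence in section 6.0 applies, that recruitment sex is available for those affected, and that the DAG retains sex. The last is near certain, given its listing in sections 8.1.3 and 8.2.

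**What to change.** Replace the definition in section 11.1.1 with wording such as: *Sex as recorded at recruitment will be the covariate and subgroup variable in all non-genetic analyses. Genetic sex will be used for the discordance exclusion in section 3.1, where available, and for the SNP analyses.* It would help to state in section 3.1 which two sex variables are compared.

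The cost is one line of SAP text and no extra data. The downside is that concordance cannot be checked in participants without genotype data. Any misclassification is confined to discordant people within that subset, and I regard the risk as negligible.

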11.1.2 Anthropometrics

Body mass index (BMI), height, and weight

Body weight and standing height were measured at the assessment centre visit at recruitment. BMI was calculated as a participant’s body weight (kg) divided by the square of their height (m).

Other body composition measures

Bioimpedance was measured at the assessment centre visit at recruitment using the Tanita Bc418ma bioimpedance device, from which body fat percentage, whole-body fat mass, whole-body fat-free mass were estimated. Hand grip strength (for each hand) was measured using the Jamar Hydraulic hand dynamometer. Left calcaneal bone mineral density (BMD) was measured using a Norland McCue Contact Ultrasound Bone Analyzer, from which a heel BMD t-score was calculated for each participant. At the second instant of follow-up (2014), a dual energy X-ray absorptiometry (DXA) scan was used to measure left femoral neck BMD (from which femoral neck BMD t-scores were calculated), and total bone mineral content (BMC).

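### Region is coded only as England, Scotland or Wales, so 17 of the 22 assessment centres share one level and residual geographic differences within England are not adjusted for

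*SAP*

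**What the plan says.** Section 8.1.3 lists geography among the candidate confounders: "Potential confounders are age at recruitment, sex, region, ethnicity" and others follow. It leaves the final choice open: "The adjustment set for the adjusted model will be informed by a DAG model".

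Section 11.1.1 then fixes how region is coded. It records that "At recruitment, participants attended one of 22 assessment centres across the UK", and continues "We will group the centres into three regions as follows: England", followed by 17 named centres, then "Scotland (Edinburgh, Glasgow), and Wales (Cardiff, Swansea, and Wrexham". The result is one variable with three levels.

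Below the level of the centre, the same section provides an area deprivation score: "Each participant was assigned a score corresponding to the output area in which their postcode was located". It is used in quintiles.

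Centre appears nowhere else as a model term. The Cox models (8.1.2, 8.1.3), the mediator regressions and IORW (8.3) and the six sensitivity analyses (8.4) neither adjust for it nor stratify by it.

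The three countries also match the three hospital data sources in section 5.0, whose records end at different dates (September 2021, July 2021 and February 2018).

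**The concern.** A confounder can be adjusted for only at the resolution at which it is coded. With England as one level, the region term treats Croydon and Hounslow as the same place as Newcastle and Middlesbrough. If the proportion of vegetarians and the risk of hip fracture both vary between such places, for reasons that the other covariates do not capture, that association enters the diet-group HRs. Townsend quintile does not close the gap, because it measures deprivation and not location: two equally deprived areas at opposite ends of England get the same value.

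The pending DAG does not settle this either. It decides whether region enters the model, while section 11.1.1 has already decided its levels.

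The pescatarian and vegetarian groups (10,696 and 8,685 in section 6.0) are small, and an uneven spread across centres could affect them. A second place to look is section 8.3, where mediation is explored only if the mediator differs significantly between a diet group and regular meat-eaters. Height, weight and bioimpedance were taken at the assessment visit (11.1.2). Centre differences in these measures, from the population or from measurement, could enter the diet-group contrasts. That is a possibility and not something the SAP states.

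**Working it through.** **Count of centres.** Section 11.1.1 lists 17 English, 2 Scottish and 3 Welsh centres: 17 + 2 + 3 = 22, as stated. Full centre coding therefore needs 22 − 3 = 19 more levels.

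**Yardstick from Table 3.** Minimum detectable HR = exp[(1.960 + 0.842)/(SD × √events)], with SD = √[p(1 − p)] and each group paired with regular meat-eaters at 3% incidence. For vegetarians:
- p = 8,685/256,256 = 0.0339, so SD = 0.181
- events = 0.03 × 256,256 = 7,688
- HR = 1.193 (Table 3: 1.19)

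The same form gives 1.173 for pescatarians (1.17) and 1.049 for occasional meat-eaters (1.05). The vegetarian figure implies SE(log HR) = ln(1.19)/2.802 = 0.062.

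**Size of a possible shift: assumed, since the SAP gives no centre-level diet mix or fracture rates.** Split participants into two equal halves by centre. Let the vegetarian share differ by a factor k and the fracture rate by a factor r, with no other covariate adjusted for. If the half with more vegetarians has the lower rate, the HR is multiplied by [(k + r)/(k + 1)]/[(1 + r)/2]. If it has the higher rate, the multiplier is [(kr + 1)/(k + 1)]/[(1 + r)/2].

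| k | r | lower rate where more vegetarians | higher rate where more vegetarians |
|---|---|---|---|
| 1.5 | 1.1 | 1.040/1.050 = 0.990 | 1.060/1.050 = 1.010 |
| 2 | 1.2 | 1.067/1.100 = 0.970 | 1.133/1.100 = 1.030 |
| 3 | 1.4 | 1.100/1.200 = 0.917 | 1.300/1.200 = 1.083 |

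On the SE scale, 0.970 is |ln 0.970|/0.062 = 0.5 SE and 0.917 is 1.4 SE. Both overstate the effect on the adjusted HR, because the covariates would absorb part of the difference.

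**A second set of assumptions.** Let s be the between-centre SD of log hazard, t that of log diet odds, and ρ their correlation. The factor is about exp(ρst). Values s = 0.05, t = 0.1, ρ = 0.3 give 1.00; s = 0.10, t = 0.3, ρ = 0.5 give 1.015; s = 0.20, t = 0.5, ρ = 0.8 give 1.083. The range is again about 0% to 8%.

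**Mediator step.** Assume complete mediator data and outcomes in SD units. The vegetarian contrast then has SE = √(1/8,685 + 1/247,571) = 0.0109, so a difference of 1.96 × 0.0109 = 0.021 SD reaches p < 0.05. With two halves and k = 2, an offset d between the halves shifts the contrast by (2/3 − 1/2)d = d/6. An offset of 6 × 0.021 = 0.13 SD would produce that difference by itself. Whether offsets of this size exist is unknown.

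**Cost in precision.** Expected events are 0.03 × 472,337 = 14,170. That is 14,170/22 = 644 per centre if centres were of equal size, of which about 12 would be in vegetarians (0.03 × 8,685/22). The share of exposure variance lying between centres is about p(1 − p)t². At t = 0.3 it is 0.003 for vegetarians and 0.022 for occasional meat-eaters; at t = 0.5 it is 0.008 and 0.062. The SE grows by the factor 1/√(1 − share), at worst 1/√(1 − 0.062) = 1.03, and less in practice because the country term already removes some of this variation.

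**The case against.** The strongest reply is that nothing here is wrong. The SAP contradicts no other passage and misstates no figure. Country is a coherent coding, it follows the hospital data sources, and the adjustment set is still open. Centre is also largely a proxy for who lives there, and the plan measures much of that directly: Townsend by output area, ethnicity, education, smoking, alcohol, physical activity, BMI and chronic disease, with attained age as the timescale.

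Much of this stands. It makes the point a refinement, and it rules out four stronger readings that a reader might infer:

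- *That centre differences stay wholly uncontrolled.* They do not. Only the part left after Townsend quintile and the individual covariates is unadjusted.
- *That different staff and devices at each centre bias the results.* The SAP does not say that staff or units differed. Section 11.1.2 names one device model per measure, for instance "Hand grip strength (for each hand) was measured using the Jamar Hydraulic hand dynamometer". Measurement offsets also cannot reach the exposure (a touchscreen questionnaire) or the outcome (hospital inpatient records). They could matter only through measured BMI or in the conditional mediation step.
- *That the vegetarian HR is biased downwards to 0.92.* That figure needs a threefold share ratio and a 1.4 rate ratio together, no covariate adjustment, and one chosen direction. It does not estimate bias in the adjusted HR.
- *That the centre code is discarded.* The SAP defines a grouping; it does not say that the underlying variable is dropped.

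One part of the reply does not stand. Matching the censoring dates is a reason to keep country for censoring, and no reason to use the same coarse variable as the confounder.

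**Conclusion.** The point holds in a limited form. Region as coded gives no geographic control within England, where 17 of the 22 centres lie, beyond Townsend quintile and the individual covariates. No sensitivity analysis checks whether that matters.

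The size cannot be computed from the SAP. Under crude two-group assumptions the vegetarian HR would move by about 1% to 8% in either direction, and by less once the other covariates are in the model. Even the largest of these shifts is smaller than the detectable effects for pescatarians (1.17) and vegetarians (1.19). In the second set of assumptions, whose formula applies to any diet group, only the more extreme values pass the 1.05 for occasional meat-eaters. Per-centre event counts assume equal centre sizes, which the SAP does not give.

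This is a coarse covariate choice that can be refined at almost no cost. It does not threaten the main analysis.

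**What to change.** In sections 8.1.2 and 8.1.3, stratify the Cox models by assessment centre (22 levels), or enter centre as a 22-level factor, in place of the three-level region. Centre is nested within country, so no control that region provides is lost. In section 8.3, put the same term in the mediator regressions and the IORW models. In section 11.1.1, keep the England/Scotland/Wales grouping only to assign the hospital-data censoring date.

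If the sponsor prefers to keep the three-level region in the main model, a centre-stratified version in section 8.4 is the minimum.

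The cost is a few lines of SAP text and one changed variable in the code. No new data are needed, since the grouping is built from the centre attended. The 19 extra levels are few against about 14,170 expected events.
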